Feasibility RCTs: Feedback from AAs with HTN and their health care providers guided development, pilot testing and refinement followed by repeated feasibility RCT testing and refinements of a culturally tailored mHealth MA and BP control program for AAs called Smartphone MA Stops Hypertension (SMASH).²⁰⁻²⁶ SMASH consists of multi-level components: Patient level components include: a) sequential automated reminders from an electronic med tray (blinking light, audio chime, automated call) and b) tailored SMS/voice mail that addresses: 1) motivational and social reinforcement to enhance and sustain adherence; 2) BP monitoring reminders; 3) HTN education and functional health literacy, tips on talking with doctor, etc. Provider level components include: a) weekly summary reports of subjects’ MA and BP levels with JNC8 stepped care guidelines and b) phone alerts to clinic nurse managers when verified out of range BPs occur. Our 3 feasibility trials (3 mos; 6 mos) with AAs with uncontrolled HTN demonstrated high acceptability, self-efficacy for following medical regimen, improved real-time MA, reduced emergency department use and higher percentages reaching JNC8 standard for BP control compared to standard of care (SC) cohorts.²²⁻²⁶ SMASH appears promising but requires further evaluation and refinement. *PA-14-334, Practical Interventions to Improve MA seeks testing of novel, theory guided interventions to improve MNA (self-report & objective indices required) and inclusion of a biological indicator (e.g., BP) expected to be effected by changes in adherence.* We propose to conduct a multi-site cluster efficacy RCT with 192 AAs (21-59 years old) with sole diagnosis of uncontrolled HTN and verified MNA randomly assigned to a 6-month intervention with 12-month follow-up. Evaluations will occur at baseline and months 3, 6, 12, and 18. The central hypothesis is, compared to an enhanced SC group, the SMASH group will exhibit significantly improved MA and resting and 24 hour BP control over the active treatment period (primary endpoint).

Specific aims will assess the efficacy of the SMASH intervention on:

AIM 1) Primary Outcomes: a) Medication adherence: % with electronic monitor-derived adherence scores >0.90; b) BP control: % meeting JNC8 defined BP control (resting BP<140/90 mmHg.)

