Smashers will complete the values, beliefs and life goals questionnaire (VBG; see Appx. 14). Responses are used in a tree-structured algorithm to select tailored motivational and positive reinforcement SMS or voicemail messages based on previous day’s MA levels. Examples of motivational messaging based upon patients’ responses are provided in C.1.5 and Appx. 4. After 2 consecutive weeks of 100% MA (typically first 2-4 weeks), messages are switched from daily to a variable interval schedule averaging 2 messages/week. Cumulative MA graphs will be sent on their phones weekly during the 6-month trial (MA rate algorithm in Appx. 2). Automated SMS messages will remind subjects to self-measure BP every 3 days. After each BP session, the SMASH app provides audio and visual BP feedback, and opportunity to see BP averages charted over time and against JNC8 guidelines (screenshot example in Appx. 25).

SMASHers will receive 30-45 sec audio or SMS messages 2x/week on HTN facts (e.g., HTN is permanent, uncontrolled HTN is silent killer), importance of timely, consistent MA, tips on expressing questions /concerns with MD (e.g., side effects; examples in Appx. 26). SMASHers will have auto dial feature on their app for [name] (or TACHL service techs if needed) to address technology related issues should they arise.

D.5.b. Provider Level: SMASH primary providers will receive summary reports, designed by them, using patient ID#s every week based upon their preference (e.g., email; NexGen EMR with email reminder to view it; example in Appx. 27). They will receive email reminders for viewing generated reports as needed every 6 hrs for 24hr period. They (and the SC MDs) will receive the same summary charts of JNC8 BP management guidelines used by us in other studies^{22,23,25} (Example in Appx. 28). If a SMASHer’s mean BP exceeds thresholds (e.g., BP >180/ 105 or <100/75 mmHg) during a session, [name] will receive an SMS alert, call the patient and conduct the BP protocol again. If BP still exceeds thresholds, FQHC providers have requested their nurse managers be called to do a follow-up with the patient.

D.5.c. Enhanced Standard Care (SC) Protocol: Subjects whose practice site is randomized to the SC group will continue to use the tray with reminder functions disabled for another 6 months. To **help maximize rigor**

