
For AIMS 2: secondary outcomes (changes in SDT constructs [i.e., competence & autonomous motivation], % reaching & sustaining 24-hr BP control [<130/80 mmHg], therapeutic inertia (i.e., % making med change in patient's EHR & script delivery to patient or pharmacy within 24 hours of subject's clinic visit and/or receiving BP info report)⁷² and **AIM 3: exploratory outcomes** (cost effectiveness; changes in TC, LDL, HgA1c, blood glucose) in the intent-to-treat sample, we have 80% power to detect a difference of 0.53 sd between the 2 groups assuming $\alpha = 0.05$ (Type I error rate), two sided; independent sample t-test comparison of means; equality of variance between groups. For 24-hour BP, we will have > 85% power to detect a 30% difference in % reaching 24-hr BP control between groups. Our 24-hr BP data from a subgroup (N=12) of FQHC AAs in the feasibility trial found 85% of the SMASH group vs 25% of the SC group achieved 24-hr BP control at 6 mos.

D.9. Data Management & Quality Control: Quality control checks of anthropometrics/BP evaluations & 24-hr BP protocol delivery will be run on random selection of 10% of subjects per mo & protocol retraining conducted as needed. Questionnaire data will be directly captured via REDCap (HIPAA compliant, web-based app) & overseen by [name] and [name]. Clinic data (e.g., anthropometrics, BP) & EMR derived data (e.g. TC, HgA1C) will be double entered with discrepancies resolved by [name]. Data will be reviewed on twice-monthly basis. Outlying, inconsistent data values, as well as missing data, will be targets of the data quality review. Issues will be communicated to Drs. [name], [name] and [name] for resolution.

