The practice sites will have been randomly assigned to SMASH or SC. The MDs and nurse managers at each site will have received an orientation in the SMASH study and refresher on the JNC8 Guidelines for HTN management. **As in our feasibility trials, the project research technicians responsible for conducting all evaluations will remain blinded to the subjects' status for the entire duration of the study and follow-up.** To help prevent contamination, the SMASH and SC subjects will be reminded by phone the night before study evaluations by [name] and again in clinic by the nurse manager, not to discuss their involvement in the trial with the technicians. Subjects will also be instructed not to discuss their treatment regimen with other individuals excepting those in their household. **The SMASH project manager, [name], will not be directly involved with data collection, as she will be a phone contact for SMASH subjects and will not be blinded.** This same approach was successful in the 6-month FQHC feasibility trial.

Primary clinical outcome variables are 1) fraction of subjects reaching JNC8 guidelines for BP control (i.e., resting BP $< 140/90$ mmHg), and 2) fraction of subjects with medication adherence score > 0.90 , as measured by electronic medication tray. Secondary clinical outcome measures include provider adherence to JNC8 guidelines, as measured by timing of medication changes, % reaching 24-hr ambulatory BP control (BP $< 130/80$ mmHg) and changes in subjects' SDT constructs of competence and autonomous motivation. Exploratory outcome variables will include cost effectiveness, other MA indices (i.e., pharmacy record based medication possession ratio [MPR] and self-report [Morisky scale]) and examination of potential moderators (e.g., gender, age, income, etc.) and mediators (e.g., competence, autonomous motivation, perceived disease severity, med side effects, depressive symptoms, sleep quality, etc.) on MA and BP control. We will also explore impact of SMASH program (i.e., increases in MA) upon changes in physical risk factors of TC, LDL, HgA1c and blood glucose. All data will be evaluated on an intent-to-treat basis.

Inclusion Criteria:

1. 21-59 years old; male or female; African American or Black
2. Prescribed medication(s) only for HTN;
3. Medication possession ratio (MPR) $< .85$ for last 3 months;

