The MUSC IRB has approved the use of SMASH, the various study procedures, and the ICD. The practice site MDs and nurse managers maintain CITI certification. Several Fetter Health Care Network (FHCN) MDs are quite familiar with SMASH, as they jointly participated in the development of the provider portion of the program. They helped design the MD summary report contents and how such a program can best function given the way their FHCN center (and other FQHCs) operate. They will receive training from the PI, [name], project manager, [name], and Co-I, [name], on the rationale for the SMASH efficacy trial and how the programs will operate. The SMASH project manager, [name], will contact potentially eligible patients by phone to gauge their interest. If they express an interest in participating, they will be invited to an initial screening at the FHCN clinic. She will explain the risks and benefits of study participation at the time of their screening visit. Interested participants will have all of their questions answered and will sign a written informed consent document. All participants will be reminded that they are free to contact study personnel or the PI at any time if any questions or concerns arise. They will be provided a copy of the written consent with the SMASH project with contact information for the project manager, the PI, and the MUSC IRB Chair.

b. Protections Against Risks

All the material delivered to the SMASH cohort by smart mobile phone and to the SC cohort either by mobile phone or hard copy mail are hygienic and health promoting and non-invasive with no known adverse physical side effects and present no more than minimal risk to the subject. With exception of standard of care blood draws, the study procedures are non-invasive and present no more than minimal risks to the subject. Subject data will be stored with coded ID numbers and no identifiers will accompany the data files. Confidentiality will be maintained. [name] will keep all records in locked storage areas and on encrypted network storage.

3. Potential Benefits of the Proposed Research to Human Subjects and Others

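### Provider orientation to SMASH is not limited to SMASH clinics, and the plan never says that SC doctors receive no tray reports, although timely medication change by these doctors is a secondary outcome.

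*Combined protocol and SAP*

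**What the plan says.** Protection of Human Subjects 1.a states: "The practice sites will have been randomly assigned to SMASH or SC". The next sentence begins: "The MDs and nurse managers at each site will have received an orientation in the SMASH study and refresher on the JNC8 Guidelines". Section 2.a adds that several doctors in the network "jointly participated in the development of the provider portion of the program", that "They helped design the MD summary report contents and how such a program can best function", and that training will be given "on the rationale for the SMASH efficacy trial and how the programs will operate".

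Specific Aims describes the SMASH provider component as weekly summaries of "MA and BP levels with JNC8 stepped care guidelines", plus phone alerts for verified out-of-range readings. D.5.b assigns the weekly reports to SMASH primary providers. It shares the guideline chart across arms: "They (and the SC MDs) will receive the same summary charts of JNC8 BP management guidelines used by us in other studies".

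D.3.b, which covers everyone in the one-month tray screening, has subjects told that their doctors will be sent summaries of their medication-taking pattern. D.5.c keeps SC subjects on the tray, reminders off, for another 6 months.

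The provider outcome is defined in D.8 (Aim 2) as the percentage "making med change in patient's EHR & script delivery to patient or pharmacy within 24 hours" of a clinic visit and/or a BP report. D.10 (Aim 2) uses the same 24-hour criterion.

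**The concern.** Randomising by clinic is meant to keep the provider component of SMASH away from SC doctors. That component exists to reduce therapeutic inertia (A.4), and the secondary outcome measures the same behaviour in the same doctors. If SC doctors are taught why SMASH is being tested and how its provider side works, some may act faster on high readings whatever their arm. If they also receive summaries of their patients' tray data, they hold adherence information that enhanced SC is not described as providing.

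Either route would narrow the arm difference on provider adherence. It would also narrow the difference in BP control, to the extent that BP control works through prescribing. A null provider result could then mean that the component does not work or that SC moved toward SMASH, and the plan collects nothing to separate the two.

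**Working it through.** The plan states no contamination rate, so there is no figure to reproduce. The check sets the sections side by side.

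1. **Who is oriented.** The all-site statement is in 1.a. It follows directly on the sentence assigning sites to either arm, so its reference to each site includes SC. Section 2.a alone would not establish this: the pronoun opening its training sentence may mean the co-designing doctors, or all site doctors and nurse managers. On either reading, nothing confines the training to SMASH clinics.

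2. **When.** Neither section says whether training follows site assignment. Training given before assignment could not differ by arm.

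3. **What is shared and what is withheld.** Shared by design: the JNC8 refresher (1.a) and chart (D.5.b). Described for SMASH only: weekly patient reports and out-of-range alerts (Specific Aims, D.5.b). Not settled: how much of the SMASH rationale and operation SC doctors are taught.

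4. **Tray information.** D.3.b promises summaries to subjects' doctors before subjects enter the trial, with no limit by arm. D.5.c continues the tray in SC. No section says whether SC doctors receive tray summaries, in screening or afterwards.

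5. **Link to an outcome.** Table 3 takes the provider outcome from weekly reports for SMASH subjects and from clinic visits for all subjects. The clinic-visit part is where a change in SC doctors' behaviour would show.

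6. **Safeguards.** Section 1.a tells subjects not to discuss their regimen outside the household and keeps technicians blinded. No measure covers providers, and D.10 does not mention provider contamination.

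7. **Co-designers.** Their number, clinics and arms are not given. Assume they work at k different clinics and that allocation is a simple 4:4 split of 8. The chance that at least one of those clinics is in SC is 1 − C(8−k, 4−k)/C(8, 4):
   - k = 1: 1 − 35/70 = 50%
   - k = 2: 1 − 15/70 = 79%
   - k = 3: 1 − 5/70 = 93%

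   These are chances under an assumption, not evidence that any co-designer is in SC.

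8. **Size.** If a share c of the provider effect D reached SC, the expected difference would be (1 − c)D. The documents give no c. For an assumed c of 10% to 30%, between 90% and 70% of D would remain. I do not turn this into power. The 30-point difference in D.8 belongs to adherence, BP control and 24-hour BP control, and the ICC of 0.04 is stated for the primary outcomes. The only medication-change rate in the documents, 13% of visits with uncontrolled BP (A.4), comes from a cited cohort. The one power statement covering therapeutic inertia (D.8: 80% for 0.53 sd) makes no allowance for contamination.

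**The case against.** The strongest reply is that knowing about SMASH is not receiving it. An SC doctor who knows that weekly reports exist still has none to act on, and the report-triggered part of the outcome cannot arise in SC on the plan as described. An orientation in the study may mean trial procedures. Section 2.a refers to programs in the plural, and 1.c names the two as SMASH and enhanced SC, so the training may be even-handed. Some awareness is unavoidable, because primary care providers must assent to each patient's participation. Clinic randomisation already limits sharing, the outcome is secondary, any bias runs toward no difference, and tray-measured adherence is patient behaviour.

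Most of this stands, and it rules out several stronger readings that a reader might infer:

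- **SC doctors receive the weekly SMASH reports.** Not shown; D.5.b gives them to SMASH providers. What remains open is the wider promise in D.3.b.
- **Co-designers sit in SC clinics.** No section places one there. D.5.b, read literally, ties report design to SMASH providers.
- **The JNC8 chart and refresher are contamination.** They are a deliberate part of enhanced SC.
- **A definite loss of power.** The inputs are borrowed from other outcomes and c has no source.

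The reply does not supply a limit on what SC sites are taught, a statement that SC doctors get no tray data, or a provider-level safeguard.

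**Conclusion.** The point holds in limited form. The documents establish an all-site orientation in the SMASH study, training not restricted by arm, a promise of medication-taking summaries that does not distinguish arms, and no provider-level safeguard. The behaviour concerned is itself a secondary outcome. The likely direction is toward no difference on provider adherence, with a smaller effect on BP control.

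This assumes that awareness, or any tray reports that SC doctors receive, changes how quickly they adjust medication. The plan neither supports nor excludes that. The size cannot be derived from the documents. This is a cheap improvement that protects the reading of one secondary outcome; it does not undermine the primary adherence comparison.

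**What to change.** - After site assignment, give training on the SMASH rationale, provider reports and operation only to the 4 SMASH sites. Give SC sites trial procedures, the SC programme, and the JNC8 refresher and chart only. Say in 1.a and 2.a who is trained, in what, and when.
- State in D.5.c that SC providers receive no tray or adherence reports during the 6-month trial, and align the D.3.b wording given to subjects with this.
- Record by arm which study providers co-designed the provider component. Pre-specify a sensitivity analysis of the provider outcome that excludes co-designers' patients in both arms. Excluding them from SC alone would be an asymmetric exclusion after randomisation.

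I would not add a rule replacing co-designers at SC clinics. Two providers are needed per site, and 7 of the 8 clinics average 2.4 (Introduction to Revised Application), so there is seldom a substitute.

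Cost: a second training script and one extra analysis, with no added patients. D.1 gives each provider 12 study patients, so each excluded provider removes about 12 of the 96 in that arm (12/96 = 12.5%), in the sensitivity analysis only.

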Description: (The purpose of TSRQ is to assess the degree to which one's motivation for a particular behavior or set of behaviors is relatively autonomous or self-determined, (of if motivation is externally driven (controlled)). The responses on the autonomous items are averaged to form the reflection of autonomous motivation for the target behavior and the responses on the controlled items are averaged to form the reflection of controlled motivation for the target behavior. (In those studies where a motivation has also been assessed, the amotivated responses are also averaged. These three subscale scores can be used separately, or a Relative Autonomy Index can be formed by subtracting the average for the controlled reasons with the average for the autonomous reasons. (Autonomous: (1, 3, 6, 8, 11, 13) (Controlled: (2, 4, 7, 9, 12, 14) (No motivation: (5, 10, 15))

(

((

(

1. Source: (Williams GC et al. (1996) Motivational predictors of weight loss and weight loss maintenance, Journal of Personality and Social Psychology, (70), (115) 26.

(

Sample Characteristics: (94 obese individuals who enrolled in a weight loss program. ((27% male (Mean age 43.4 (Range: (20-77))

(

Psychometric Properties: (Reliability: (Test Retest (coefficient (after 18 months (or more) (Autonomous items: $r = .47$ ($p < .01$), (Controlled items: $.34$ ($p < .05$)).
Validity: (Autonomous items correlated with Autonomy orientation score of General Causality Orientations Scale ($r = .38$, $p < .001$) and the Perceived Autonomy Support of the Health Care Climate Questionnaire ($r = .38$, $p < .001$).
Predictive Value: (Autonomous items at start predicted attendance ($r = .34$, $p < .001$) and BMI ($r = .11$, $p < .05$)).

(

2. Source: (Williams GC et al. (1998) Autonomous regulation and long term medication adherence in adult outpatients, Health Psychology, (17), (269) 276.

(

Sample Characteristics: (126 Adults taking at least one prescription pill ((24.6% male, (mean age 56.3 years, (range: (37-85))

Psychometric Properties: (Reliability: (Internal consistency: (Cronbach's alpha score, (Autonomous items = $.81$, (Controlled items = $.84$)
Validity: (Autonomous items correlated with the Perceived Autonomy Support of the Health Care Climate Questionnaire ($r = .24$, $p < .05$).
Predictive Value: (Autonomous items predicted adherence ($r = .58$, $p < .0005$)).

(

(

Medication Adherence (ASRQ)

The following questions relate to the reasons why you would either start to take your medicine as prescribed by your physician or continue to do so.

Different people have different reasons for taking medicine as prescribed, and we want to know how true each of the following reasons is for you. Please indicate the extent to which each reason is true for you.

All 15 responses are to the one question:

The reason I would take my medicine as prescribed by my physician is:

1. Because I feel that I want to take responsibility for my own health.

						
1	2	3	4	5	6	7
Not at all		Somewhat		True		Very True
True		True				

2. Because I would feel guilty or ashamed of myself if I did not take my medicine as prescribed.

						
1	2	3	4	5	6	7
Not at all		Somewhat		True		Very True
True		True				

3. Because I personally believe it is the best thing for my health.

						
1	2	3	4	5	6	7
Not at all		Somewhat		True		Very True
True		True				

4. Because others would be upset with me if I did not.

						
1	2	3	4	5	6	7
Not at all		Somewhat		True		Very True
True		True				

5. I really don't think about it.

						
1	2	3	4	5	6	7
Not at all		Somewhat		True		Very True
True		True				

6. Because I have carefully thought about it and believe it is very important for many aspects of my life.

						
1	2	3	4	5	6	7
Not at all		Somewhat		True		Very True
True		True				

7. ~~Because I would feel bad about myself if I did not take my medicine as prescribed.~~

1

Not at all
True

2

Somewhat
True

3

4

5

True

6

7

Very True

8. ~~Because it is an important choice I really want to make.~~

1

Not at all
True

2

Somewhat
True

3

4

5

True

6

7

Very True

9. ~~Because I feel pressure from others to do so.~~

1

Not at all
True

2

Somewhat
True

3

4

5

True

6

7

Very True

10. ~~Because it is easier to do what I am told than to think about it.~~

1

Not at all
True

2

Somewhat
True

3

4

5

True

6

7

Very True

11. ~~Because it is consistent with my life goals.~~

1

Not at all
True

2

Somewhat
True

3

4

5

True

6

7

Very True

12. ~~Because I want others to approve of me.~~

1

Not at all
True

2

Somewhat
True

3

4

5

True

6

7

Very True

13. ~~Because it is very important for being as healthy as possible.~~

1

Not at all
True

2

Somewhat
True

3

4

5

True

6

7

Very True

14. ~~Because I want others to see I can do it.~~

1

Not at all
True

2

Somewhat
True

3

4

5

True

6

7

Very True

15. ~~don't really know why.~~

1

Not at all
True

2

+

3

Somewhat
True

4

+

5

True

6

7

Very True

+

Medication Adherence Self Efficacy Scale Revised (MASESR) (Fernandez, et al., (2008)

Description: (The Medication Adherence Self Efficacy Scale (MASESR) consists of 13 self-administered questions, which measure situation-specific efficacy beliefs regarding adherence to prescribed antihypertensive medications. Responses are Not at all sure (=1, A little sure (=2, Fairly sure (=3, Extremely sure (=4. ((

1. (Fernandez(S, et al. ((2008) (Revision and validation of the medication adherence self efficacy scale (MASES) in hypertensive African Americans. Journal of Behavioral Medicine, 31(6), 453-462
Sample Characteristics: ((168 hypertensive African Americans ((14% (male) (mean age 54 ((±12.4) (years. ((

+ Psychometric Properties: ((Reliability: (Chronbach's alpha (= .92 (Test-Retest ((3 months) (coefficient (= .51 ((p < .001). ((
Concurrent Validity: (With self-report of adherence, (Non-adherent (Mean (= 3.51 (±.52, (adherent (Mean (= 3.81 (±.33 ((p < .001) ((
With electronic adherence measure (MEMS) at 3 months: (r (= .20, (p (= .02. ((
Predictive validity: (Baseline MASESR (with MEMS) at 3 months: (r (= .19, (p (= .02. ((

2. (Voils(C, et al., ((2012) (Initial Validation of a Self-Report Measure of the Extent of and Reasons for Medication Nonadherence. Med Care, 50, 1013-1019. ((
Sample Characteristics: ((202 hypertensive veterans ((86% (male), (mean age 64.1 ((±11) (years, (50% (Black. ((

(Psychometric Properties: ((Concurrent validity: (with Extent of Nonadherence measure: (r (= .42, (p < .0001. ((

+ 3. (Breaux-Shropshire(T, et al., ((2012) Relationship of Blood Pressure Self-Monitoring, Medication Adherence, Self-Efficacy, Stage of Change, and Blood Pressure Control Among Municipal Workers With Hypertension. Workplace Health & Safety, 60(7), 303-311. ((

Sample Characteristics: ((149 hypertensive municipal employees ((85% (male), (mean age 47 ((±8.4) (years, (69% (Black. ((

(Psychometric Properties: ((Concurrent validity: (with Morisky Medication Adherence Scale: (r (= .549, (p < .001. ((

+
+ +

+

MASES]R+

+

Situations come up that make it difficult for people to take their medications as prescribed by their doctors. Below is a list of such situations. We want to know your feelings about taking your blood pressure medication(s) in each of these situations. Please indicate your response by checking the box that most closely represents your feeling. There are no right or wrong answers.

For each of the situations listed below, please rate how sure you are that you can take your blood pressure medications all of the time.

Items+	Not at all sure+	A little sure+	Fairly sure+	Extremely sure+
How confident are you that you can take your blood pressure medications:+				
1. When you are busy at home	((((((((
2. When there is no one to remind you	((((((((
3. When you worry about taking them for the rest of your life	((((((((
4. When you do not have any symptoms	((((((((
5. When you are with family members	((((((((
6. When you are in a public place	((((((((
7. When the time to take them is between your meals	((((((((
8. When you are travelling	((((((((
9. When you take them more than once a day	((((((((
10. When you have other medications to take	((((((((
11. When you feel well	((((((((
12. If they make you want to urinate while away from home	((((((((
Please rate how sure you are that you can carry out the following task:+				
13. Make taking your medications part of your routine	((((((((

(

+

+
